Completion of patient participation ¹⁵										X
Vital status collection ¹⁶										X

Footnotes:

1. Vital signs measurement shall include BP measurement, body temperature, respiratory rate and pulse rate.
2. In addition to the scheduled ECGs (electrocardiograms), ECGs should be done and documented at any time of clinical event (e.g. acute event of arrhythmia, tachy- or bradycardia, angina, or MI).
3. Randomisation of patients shall happen not later than 24 hours after the confirmation of the inclusion and exclusion criteria. Study drug administration shall start within 6 hours of the randomisation. The time-point of obtaining D-Dimer levels can be as long as four calendar days before screening.
4. In Part 2: Initial i.v. infusion of alteplase 0.6 mg/kg over 2 hours (Day 1) immediately followed by daily i.v. infusion of 0.04 mg/kg/hour over 12 hours (starting on Day 1 and up to Day 5 at maximum, plus possible interruption time for urgent reasons). Interruptions up to 72 hours in total for urgent reasons are allowed and accordingly, the time window of the visits may be extended. The very first infusion of alteplase should start at least 10 hours after the last injection of a LMWH. Each daily 12-hour infusion of alteplase is followed by an interruption of approximately 12 hours. Does not apply for SOC treatment arm.
5. PK samples collection (on a voluntary basis, 1st sample: prior to first drug administration on Day 1 (Visit 2a pre-dose) (planned time: -1:00 h; time window -2:00 h to just prior drug administration), 2nd sample: at steady state of the initial i.v. infusion on Day 1 (Visit 2a post-dose initial i.v. infusion) (planned time 1:30 h; time window: between 1:00 h after start of initial i.v. infusion and just prior to end of initial i.v. infusion), 3rd sample: at steady state of the long-term i.v. infusion on Day 1 (Visit 2a post-dose long-term i.v. infusion) (planned time: 6:00 h; time window: between 2 h after start of long-term i.v. infusion and just prior to end of long-term i.v. infusion) For further details refer to [Section 5.3.1](#). Separate informed consent has to be signed before including patient in PK collection.
6. On Day 6 only lab samples required for SOFA score and PaO₂/FiO₂ shall be collected.
7. D-dimer levels shall be measured at Day 0 (or no more than 4 calendar days before screening), days 3, 5, 7 and 28

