The most common AEs by system organ class were: respiratory, thoracic and mediastinal disorders (alteplase 0.3/0.02 mg/kg: 7 patients/35.0%, alteplase 0.6/0.04 mg/kg: 12 patients/60.0%, SOC: 9 patients/40.9%), infections and infestations (9 patients/45.0%, 4 patients/20.0%, 11 patients/50.0%), and general disorders and administration site conditions (7 patients/35.0%, 7 patients/35.0%, 4 patients/18.2%).

Serious AEs reported for >2 patients in a treatment group were respiratory failure (alteplase 0.3/0.02 mg/kg: 2 patients/10.0%, alteplase 0.6/0.04 mg/kg: 0 patients, SOC: 6 patients/27.3%), pulmonary embolism (2 patients/10.0%, 3 patients/15.0%, 1 patient/4.5%), septic shock (1 patient/5.0%, 0 patients, 4 patients/18.2%), and epistaxis (3 patients/15.0%, 1 patient/5.0%, 0 patients).

Treatment-emergent bleeding events were more frequent in the alteplase treatment groups, both for any bleeding events and major bleeding events. Major bleeding events up to Day 6 were reported only in the alteplase treatment groups (1 patient in the 0.3/0.02 mg/kg dosing group and 4 patients in the 0.6/0.04 mg/kg dosing group). Most bleeding events until Day 12 were non-major (4 patients, alteplase 0.3/0.02 mg/kg; 9 patients, alteplase 0.6/0.04 mg/kg; 3 patients, SOC group). There were no fatal bleeding events.

The study results of Part 1 support the continuation of the study into Phase III (Part 2), implementing a comparison of the alteplase 0.6/0.04 mg/kg dose versus SOC alone.

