3.3.4.1 Discontinuation of trial treatment

An individual patient will discontinue trial treatment if:

- The patient wants to discontinue trial treatment, without the need to justify the decision.
- The patient needs to take a concomitant medication that interferes with the investigational medicinal product (IMP) or other trial treatment. Please refer to [Section 4.2.2](#) for restricted medications during this trial.
- The patient can no longer receive trial treatment for medical reasons, such as surgery, adverse events, etc. including:

- safety reasons, such as active bleeding, or any other condition that is considered a safety risk at the discretion of the investigator
- in case of clinical improvement of respiratory situation with sustained (as per investigator's judgement) $\text{PaO}_2/\text{FiO}_2$ ratio above 300.
- Need for ECMO or RRT. No additional dose of alteplase 0.3 mg/kg/2 h or 0.6 mg/kg/2 h (Part 1) or 0.6 mg/kg/2 h in Part 2 should be given under these circumstances.

Recommendation for temporary interruption of alteplase daily infusions:

- Interventions (e.g. insertion of lines, catheters, drains and tubes) during the treatment period with alteplase should be avoided, whenever possible. If absolutely necessary, they need to be performed in the alteplase infusion-free interval (i.e. in the 12-hours break between two infusions) and ideally not on the first day.
- Alteplase infusion can be resumed at least 6 hours after the intervention. This duration can be extended in case of complications during the intervention.
- If the fibrinogen level decreases to levels <150 mg/dL. The infusion should be restarted when fibrinogen level is 150 mg/dL or higher [[c32479735-01](#); [P13-13102](#)]
- Interruptions for unavoidable interventions, drop in fibrinogen level or bleeding (beyond the 12 hours alteplase infusion-free interval per protocol) are allowed for up to a maximum of 72 hours. The time window of the subsequent visits and infusions may be extended accordingly. It is preferable to achieve normal haemostasis parameters before the next infusion of alteplase.

If new efficacy/safety information becomes available, BI will review the benefit-risk assessment and, if needed, pause or discontinue the trial treatment for all patients or take any other appropriate action to guarantee the safety of the trial patients.

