Posology:	
Dose of Long-Term i.v. infusion in Part 1:
 
Dosing regimen A: 0.02 mg/kg/hour given over 12 hours Dosing regimen B: 0.04 mg/kg /hour given over 12 hours
 
Dose of Long-Term i.v. infusion in Part 2:
 
One dosing regimen is carried forward based on results from Part 1 and recommendation by the DMC. Dosing regimen B: 0.04 mg/kg /hour given over 12 hours
 
Optional additional i.v. infusion (allowed one time, during Days 2 to 5):
 
Part 1: One optional additional i.v. infusion: Dosing regimen A: 0.3 mg/kg given over 2 hours
 
Dosing regimen B: 0.6 mg/kg given over 2 hours
 
This additional i.v. infusion can be given one time during Days 2 to 5 in case of clinical worsening (as per investigator judgement)
 
Please note: This optional single additional infusion of alteplase may only be given one time. This additional dose may be administered on either Day 2, 3, 4, or 5. The duration of the long-term infusion (0.02mg/kg/h over 12 hours in Dosing regimen A; 0.04mg/kg/h over 12 hours in Dosing regimen B) on the day of optional

Table 4.1.1:1

Test product (cont)

Substance:	Alteplase (recombinant tissue plasminogen activator)
Pharmaceutical formulation:	Powder and solvent for solution for injection/infusion
Source:	Boehringer Ingelheim Pharma GmbH & Co. KG
Unit strength:	50 mg/vial powder and 50 mL solvent
	
additional infusion should sum up to 12 hours. The long-term-infusion should not be given in parallel to the optional additional dose, but should be interrupted for approximately 2 hours, when the optional additional infusion of 0.3mg/kg/2h or 0.6mg/kg/2h is given. On the day of optional additional infusion, the total infusion time is 2 hours plus 12 hours = 14 hours.
 
For the optional additional i.v. infusion application, it is recommended that fibrinogen concentrations are \geq 300mg/dL.
 
Part 2: One dosing regimen is carried forward based on results from Part 1 and recommendation by the DMC.
 
One optional additional i.v. infusion:
 
Dosing regimen B: 0.6 mg/kg given over 2 hours
 
This additional i.v. infusion can be given once during the treatment period in case of clinical worsening (as per investigator judgement)

	
For Instructions for Preparation and Administration of Trial Medication, please see ISF.
 
For dose calculation and infusion rates, please see Appendix 10.5

Mode of administration:	Intravenous infusion

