- Before the start of the very first alteplase infusion, there should have been a time period of at least 10 hours since the last LMWH (S.C.) administration to ensure no significant overlap of the LMWH and alteplase.

Emergency procedures

Management of Bleeding during Alteplase Treatment:

- In case of bleeding, the alteplase infusion can be interrupted up to a maximum of 72 hours.
- A restart is possible, if complete haemostasis is achieved, and if lab results support a restart (fibrinogen $\geq 150\text{mg/dL}$, haemoglobin is stable, anti-Xa 4 hours after s.c. administration is < 0.5 , or aPTT ratio is < 1.5 -fold of upper limit of normal).
- In case of interruptions of more than 12 hours, the time-windows for subsequent long-term infusions move accordingly, and the last long-term infusion may be given later than day 5 in the study. In total, up to 5x long-term infusions (of 12 hours each) can be given.

Management of serious bleeding events:

In case of serious bleeding, in particular cerebral or pulmonary haemorrhage, the fibrinolytic therapy must be discontinued, and concomitant heparin administration should be terminated immediately. Administration of protamine should be considered if unfractionated heparin has been administered. In patients who fail to respond to these conservative measures, judicious use of transfusion products may be indicated. Transfusion of cryoprecipitate, fresh frozen plasma, and platelets should be considered with clinical and laboratory reassessment after each administration. A target fibrinogen level of 1g/L (100 mg/dL) is desirable with cryoprecipitate infusion. Antifibrinolytic agents should also be considered.

Beyond patient-specific risk factors for bleeding, the bleeding risk can be estimated by the plasma fibrinogen level. Fibrinogen will be monitored daily during the treatment period with alteplase, and if the level falls below 150 mg/dL , the investigator should interrupt the alteplase infusion.

The alteplase infusion can be restarted, if fibrinogen recovers to $\geq 150\text{ mg/dL}$ during the following 72 hours.

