5.2.2 Other secondary endpoints

The secondary endpoints as defined in CTP Version 3 Section 2.1.3 which are not listed under “Key secondary endpoints” will be referred to as “Other secondary endpoints”. Efficacy endpoints will be analysed on the FAS, and the one safety endpoint “Major bleeding event (MBE) until day 6” will be analysed on the Treated Set (TS).

The planned analyses of the secondary endpoints are outlined in [Section 7.5.2](#).

MBE (according to International Society on Thrombosis and Haemostasis [International Society on Thrombosis and Haemostasis (ISTH) definition (4)]) until day 6, TS, binary endpoint

If the patient has an MBE, at any timepoint up to end of day 6 then he has met this unfavorable endpoint. If it is unknown whether the patient had an MBE up to end of day 6, regardless of the reason, then it will be assumed that the patient did not have an MBE by the end of day 6. This is a safety defined endpoint and the starting point for consideration should be consistent with the ‘on treatment’ definition in [Section 6.7](#). The time period for counting events is defined in [Table 5.2.2: 1](#) below:

Table 5.2.2: 1 Time period for counting MBE up to day 6

MBE until day 6	Start point	End date
SOC patients	Randomisation date/time	Start point + 144 hrs
Alteplase patients	First administration of alteplase date/time	Latest time of: 
 ○ Start point + 144 hrs ○ Last administration of alteplase date/time + 24 hrs

[Note: 144 hrs represents 6 days]

PaO₂/FiO₂ ratio (or inferred PaO₂/FiO₂ ratio from SpO₂) change from baseline to day 6, FAS, continuous endpoint

This assessment is planned to be measured on each of days 0 to 7, and again on day 28, but only whilst the patients is still in hospital. For this endpoint, the worst (lowest) daily measurement will be used and the higher the value the better the health status of the patient.

- If the patient is still in hospital during day 6 then the day 6 value will be used
- If the patient has been discharged from hospital prior to day 6 then the value at the time of hospital discharge will be used
- If the patient has died prior to day 6 then the last value prior to death will be used
- If day 6 value is missing but Day 5 value available, the day 5 value will be used

Proprietary confidential information © 2021 Boehringer Ingelheim International GmbH or one or more of its affiliated companies

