6.7 BASELINE, TIME WINDOWS AND CALCULATED VISITS

Randomisation is defined as Day 1 and it is planned that the alteplase patients are administered their initial 2h infusion of study medication within 6 hours of randomisation, on Day 1 (Visit 2a). The last planned administration of study medication for the alteplase patients is the long term 12h infusion on Day 5.

Since all patients are on SOC and there is no clear start or stop of SOC, a fixed treatment duration will be used for all patients, for the purposes of the analyses. Therefore, endpoints referred to as ‘on treatment’ will include all relevant events from the relevant start point plus 288 hours (last planned treatment on Day 5 + 7 days of REP = 12 days = 288 hrs).

However, to take account of the fact that some patients may have had treatment interruptions, the residual effect period should be in relation to the last intake of alteplase infusion. [Table 6.7: 1](#) below outlines the time period definitions for counting on treatment safety event.

Table 6.7: 1 Time period for counting on treatment safety events

On treatment	Start point	End date
SOC patients	Randomisation date/time	Start point + 288 hrs
Alteplase patients	First administration of alteplase date/time	Latest of: 
 Start point + 288 hrs Last administration of alteplase date/time + 168 hrs

[Note: 288 hrs represents 12 days, 168 hrs represents 7 days]

According to CTP Version 3 Section 1.2, the residual effect period (REP) is 7 days.

As outlined in CTP Version 3 Section 7.2.1, the term "baseline" refers to the last observed measurement prior to randomisation on Day 1.

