7.5.2 Other Secondary endpoints

Other secondary endpoints are defined in [Section 5.2.2](#). In all cases, standard descriptive statistics will be presented, whether the endpoint is binary or continuous.

Binary safety endpoint

For the binary safety endpoint MBE up to day 6, analysed on the TS, there will be no adjustment for covariates. Therefore, the RD will be the difference between the two incidences and the p-value and 95% CI will be determined using the Chan and Zhang exact method.

For the NIV and IMV cohorts pooled, the RD 95% CI will be estimated between the two treatment arms using the same approach as for the key secondary efficacy endpoints. However, for this pooled investigation of MBE up to day 6, the baseline D-Dimer status (≥ 3 to <5 , ≥ 5 -fold ULN) and age covariates will not be included in the model. The p-value for homogeneity will be determined similarly.

Continuous efficacy endpoints

The three other secondary endpoints which are continuous in nature will be analysed using a restricted maximum likelihood (REML) based ANCOVA comparing the outcome, by treatment. The ANCOVA model will be adjusted for the default set of covariates as outlined in [Section 7](#) for the respective NIV and IMV patient cohorts. The treatment difference with 95% CI and p-values will be presented.

For the continuous efficacy endpoints, number of OFDs at day 28, and number of days in hospital, there are not expected to be any missing values by definition and as outlined in [Section 5.2.2](#).

[figure not shown]
For the continuous efficacy endpoint change from baseline in the $\text{PaO}_2/\text{FiO}_2$ at day 6, the baseline $\text{PaO}_2/\text{FiO}_2$ will also be included in the model as covariate for adjustment. For patients that have died, or who have been discharged from hospital, the handling rules are as outlined in [Section 5.2.2](#). Note, there are expected to be very few deaths or hospital discharges prior to day 6.

In addition, subgroup analyses of this $\text{PaO}_2/\text{FiO}_2$ endpoint will be conducted in the NIV patient cohort only and using the subgroups as outlined in [Section 6.4](#). An ANCOVA model will contain the baseline $\text{PaO}_2/\text{FiO}_2$, the subgroup of interest and the interaction between subgroup and treatment.

As sensitivity analyses, the unadjusted treatment effects will be estimated, using the same approach as the main analysis, but with only treatment in the model.

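### MBE until day 6 is counted for 144 h in SOC but for longer in alteplase patients with delayed infusions, so the crude risk difference compares unequal observation time

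*SAP*

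**What the plan says.** **Counting rule (Part 2 SAP 5.2.2, Table 5.2.2:1).** SOC patients are counted from randomisation for 144 h, which the table equates with 6 days. Alteplase patients are counted from first administration to the later of 144 h and "Last administration of alteplase date/time + 24 hrs". The table does not say whether this means the start or the stop of the infusion. The sentence above the table stops at the end of day 6 and mentions no extension.

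**Analysis (Part 2 SAP 7.5.2).** There is no covariate adjustment: "the RD will be the difference between the two incidences and the p-value and 95% CI" come from an exact method. The pooled NIV and IMV version sets no common window either.

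**Why infusions can run late.** The protocol flow chart places the Day 5 infusion at hours 98 to 110. Interruptions may total 72 h (synopsis; 3.3.4.1), and "The time window of the subsequent visits and infusions may be extended accordingly". Protocol 4.2.1 lets the last infusion fall after day 5: "In total, up to 5x long-term infusions (of 12 hours each) can be given". For the on-treatment window, SAP 6.7 gives the reason for following the last infusion: "to take account of the fact that some patients may have had treatment interruptions".

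**Start point.** Flow chart footnote 3: "Study drug administration shall start within 6 hours of the randomisation".

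**Earlier part of the trial.** The Part 1 SAP capped the same endpoint at midnight of Day 6.

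**The concern.** Only one arm's window can lengthen, and it lengthens because of what happens after randomisation. A difference of two crude incidences has its usual meaning only if both arms are observed for the same time. In delayed alteplase patients the extra hours collect two kinds of bleed: those caused by the late infusion, which belong in the count, and background bleeds, for which SOC has no matching hours.

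This is the only safety endpoint among the Part 2 secondary endpoints. Bleeding is the main known risk; in Part 1, "Major bleeding events up to Day 6 were reported only in the alteplase treatment groups". The endpoint is outside the confirmatory hierarchy, but its risk difference will carry a p-value and a confidence interval and will feed the benefit-risk discussion. An event labelled as until day 6 could also occur well after day 6, and the label would mean different things in Parts 1 and 2.

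**Working it through.** **1. The plan's own figure.** 6 × 24 = 144 h, as the table states.

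**2. Alteplase window.** W = max(144, E + delay + 24), where E is the hour at which last administration is taken to occur without delay. The optional 2 h infusion enters because "This additional i.v. infusion can be given once during the treatment period in case of clinical worsening", and the flow chart allows +6 h at the Day 5 visit.

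| Reading of last administration | E | Delay beyond which W exceeds 144 h | W at 24 h | W at 48 h | W at 72 h |
|---|---|---|---|---|---|
| Start of Day 5 infusion | 98 | 22 h | 146 | 170 | 194 |
| Stop of Day 5 infusion (nominal) | 110 | 10 h | 158 | 182 | 206 |
| Stop, plus optional 2 h and +6 h window | 118 | 2 h | 166 | 190 | 214 |

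In the nominal case, 110 + 72 + 24 = 206 h. That is 62 h, or 62/144 = 43%, longer than SOC. An uninterrupted course gives 110 + 24 = 134 h, so both arms then get 144 h.

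**3. Spurious part of the risk difference.** Let p be the SOC risk at 144 h. With a constant background hazard, the excess per extended patient is [1 − (1 − p)^(W/144)] − p. Multiply by f, the share of alteplase patients extended. The documents give neither f nor a Part 2 value of p. Assumed here: p = 5%, f = 10% to 30%, nominal reading.

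| Delay, same in all extended patients | Excess per extended patient | Bias in risk difference |
|---|---|---|
| 24 h | 0.47 points | 0.05 to 0.14 points |
| 48 h | 1.28 points | 0.13 to 0.38 points |
| 72 h | 2.08 points | 0.21 to 0.62 points |

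**4. Range for p.** Part 1 SOC had no MBE up to Day 6. Its size follows from the reported percentages: 9/0.409 = 11/0.500 = 4/0.182 ≈ 22. The exact 95% upper limit for 0/22 is 1 − 0.025^(1/22) = 15.4%. With p from 0 to 15.4% and f up to 30%, the bias is 0 to 0.4 points at 24 h and 0 to 1.8 points at 72 h. The anchor is loose. Part 1 counted to midnight of Day 6, which is 120 to 144 h after a Day 1 randomisation, and it mixed ventilation types.

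**5. Scale.** With 140 and 70 NIV patients and assumed risks of 15% and 5%, the 95% half-width is about 1.96 × √(0.15 × 0.85/140 + 0.05 × 0.95/70) = 7.8 points.

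**6. The opposite asymmetry.** Alteplase counting starts at first dose, up to 6 h after randomisation. This does not shorten the alteplase window, which is still at least 144 h, but any bleed in the gap is dropped.

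**The case against.** The strongest reply is that this is a design choice with a reason. Late infusions are allowed, bleeds during them are drug effects, and a fixed cut-off would lose some of them. The rule is cautious about harm, and on the assumptions above its effect is small beside the interval width. All of that stands, and it limits the weight of the point.

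The size is also less certain than the tables suggest. Interruptions are for interventions, falling fibrinogen or bleeding. A patient interrupted for an MBE has already met this binary endpoint, so the extension adds nothing for that patient. Other delayed patients may bleed more readily than the average SOC patient. The average SOC hazard could therefore be wrong in either direction. This stands too.

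Three stronger readings are tempting and are not supported:

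- A reader might infer that the SAP plans no equal-window analysis at all. Section 5.3 is not shown, and Section 7.8.1 points to it for safety endpoints including MBE, so the absence is established only for the visible text.
- A reader might take 206 h as a ceiling. It is one nominal reading among several from 194 to 214 h.
- A reader might infer that the rule hides harm or manufactures a bleeding signal. The extension can only add alteplase events, and most of what it is meant to add is real drug effect.

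What the reply does not answer is that the visible analysis gives one crude contrast over unequal time. The on-treatment window in Table 6.7:1 cannot fill the gap, because it lengthens in the alteplase arm in the same way.

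**Conclusion.** The point holds as a modest improvement. When infusions are delayed, the MBE risk difference in SAP 7.5.2 compares a fixed 144 h in SOC with a longer alteplase window. The window lengths follow from the documents. The resulting bias runs against alteplase, is probably well under one percentage point, and cannot be sized from the documents, because the share delayed, the length of delay and the Part 2 SOC bleeding risk are not given. The uncounted gap before first dose works the other way and is smaller. Neither affects the confirmatory tests.

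The undefined term matters on its own account. Reading last administration as start or stop moves the window by 12 h and the threshold for extension from 22 h to 10 h, so two programmers could derive different counts.

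**What to change.** - Keep the current rule as the on-drug safety count.
- Beside it, report the MBE risk difference over one window that runs from randomisation in both arms: 0 to 144 h, and/or a longer window that covers delayed infusions. The longer one needs at least 6 + 110 + 6 + 2 + 72 + 24 = 220 h; 240 h would do.
- If each arm's existing start point is kept, call the window equal in length, not identical.
- State whether last administration is infusion start or stop, and reconcile the end-of-day-6 sentence with the table.

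**Cost.** SAP wording and one or two extra safety tables. Adverse events are already collected from consent to end of study. Hour-based windows need onset times, while protocol 8.3.1 lists only the onset date as mandatory; the existing table has the same need.

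**Downsides.** A 240 h window runs past nominal day 6 and dilutes the early contrast. A 144 h window alone loses bleeds in late infusions. Counted from first dose, it misses part of the last infusion once the delay exceeds 144 − 110 = 34 h and all of it from 144 − 98 = 46 h. Counted from randomisation with a 6 h lag, those limits fall to 28 h and 40 h. It should therefore sit beside the current count and not replace it.

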If the patient has an MBE, at any timepoint up to end of Day 6 then he has met this unfavorable endpoint. If it is unknown whether the patient had an MBE up to end of Day 6, regardless of the reason, then it will be assumed that the patient did not have an MBE by the end of Day 6. This is a safety defined endpoint and the starting point for consideration should be consistent with the 'on treatment' definition in [Section 6.7](#), however only including events up to midnight of Day 6.

ACM at Day 28, FAS, binary endpoint

If it is unknown whether the patient was dead at end of Day 28, then it will be assumed that the patient did not die up to Day 28, regardless of the reason. This unfavorable endpoint is met if:

- the last known status of the patient is 10 on the WHO clinical progression scale by the end of Day 28, or
- vital status is dead within 28 days

ACM / MV at Day 28, FAS, binary endpoint

If it is unknown whether the patient was on MV at Day 28, it will be assumed that the patient was not on MV at Day 28, regardless of the reason. This unfavorable endpoint is met if:

- the last known status of the patient has a value of ≥ 7 on the WHO clinical progression scale, up to end of Day 28, or
- vital status is dead within 28 days

Daily average PaO₂/FiO₂ ratio (or inferred PaO₂/FiO₂ ratio from SpO₂) change from baseline to Day 6, FAS, continuous endpoint

This assessment is to be measured approximately 3-times daily on each of days 0 to 7, and again on day 28, but only whilst the patient is still in hospital. All available values on each of these days, regardless of the position of the patient when being measured, will be averaged in order to determine the daily average PaO₂/FiO₂ ratio for that patient. The higher the value the better the health status of the patient.

[figure not shown]
- If the patient is still in hospital during day 6 then the day 6 daily average value will be used, if available.
- If the patient has been discharged from hospital prior to day 6 then the daily average at the time of hospital discharge will be used as a surrogate for day 6, if available.
- If the patient has died prior to day 6 then there will be no imputation but the death handled as failure in the determination of the difference in medians and 95% CI.

[figure not shown]
Based upon this, the change from baseline for each patient will be calculated and used for the analysis.

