- If day 6 value is missing, no Day 5 value available, but day 7 available, then day 7 value will be used
- Otherwise value set to missing for that patient.

Based upon this, the change from baseline for each patient will be calculated and used for the analysis.

Number of oxygen-free days (OFD) up to day 28, FAS, continuous endpoint

For this endpoint, 'oxygen-free' is defined as free from assistance from oxygen support. The number of oxygen-free days starts from when the patient has a 'lasting' value on the WHO clinical progression scale of ≤ 4 and ends on Day 28. A lasting value of ≤ 4 means that the value cannot exceed 4 at a later timepoint. If the patient is liberated from oxygen on Day x, then the number of OFDs is 28-x. If a patient has withdrawn consent prior to day 28 then he will have a missing value for OFD. In any case, if the status of the patient at Day 28 is death, as determined from the vital status page then the OFD=0.

Length of hospital stay up to day 28, FAS, continuous endpoint

This will be determined based upon the first hospital discharge date, or discharge to another care facility. If the patient dies within the first 28 day period, then length of hospital stay is 28.

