6.6 HANDLING OF MISSING DATA AND OUTLIERS

All efforts will be made to avoid having missing data in the database, however it is inevitable that there will be missing data, by design:

- For patients that die, there will be no further data, however this irreversible unfavourable state will be taken into consideration in the determination of each of the endpoints.
- For patients that are discharged from hospital before day 28, the only additional efficacy assessment is the vital status at days 28 and 90. The fact that the patient has improved in order to be discharged from hospital prior to day 28 will be taken into account in the determination of each of the endpoints.

Handling of missing data for the endpoints are outlined in [Section 5](#), in line with the definitions of the endpoints.

Missing or incomplete adverse event (AE) dates will be computed using the BI handling rules ([7](#)).

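### No planned Part 2 analysis of the PaO2/FiO2 change to Day 6 treats an early death as unfavourable; a rank-based analysis with deaths ranked worst should be added beside the ANCOVA

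*SAP*

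**What the plan says.** Part 2 SAP 5.2.2 defines the endpoint as the change from baseline to Day 6 in the worst daily PaO2/FiO2. For early deaths it says: "If the patient has died prior to day 6 then the last value prior to death will be used". Section 7.5.2 analyses the change by REML ANCOVA with the default covariates plus baseline PaO2/FiO2. It adds no rule of its own: "For patients that have died, or who have been discharged from hospital, the handling rules are as outlined in" section 5.2.2. It also remarks: "Note, there are expected to be very few deaths or hospital discharges prior to day 6".

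Section 6.6 of the same SAP says of patients who die that "this irreversible unfavourable state will be taken into consideration in the determination of each of the endpoints", and sends the reader to Section 5 for the rules by endpoint.

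The other two continuous endpoints in 5.2.2 give death the worst score. A patient dead at Day 28 has no oxygen-free days ("as determined from the vital status page then the OFD=0"), and a death within 28 days sets length of stay to 28.

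The Part 1 SAP, for the daily-average version of this ratio, says: "If the patient has died prior to day 6 then there will be no imputation but the death handled as failure". The last value before death appears in Part 1 only in a sensitivity ANCOVA (Part 1 SAP 7.5.2).

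Protocol 7.2.3 prescribes the covariate-adjusted REML ANCOVA for continuous endpoints, calls that analysis non-confirmatory, and does not say how deaths enter this endpoint.

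**The concern.** A patient who dies before Day 6 is scored like a survivor with the same last reading. If that reading was stable or improved, the death enters the comparison as a neutral or good result. A fatal bleed need not be preceded by worsening oxygenation. If no ratio was recorded after baseline, the last value could be the baseline itself, giving a change of 0. Entry to the FAS requires a post-baseline WHO score, not a post-baseline ratio, so this case can arise.

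At stake is how this one endpoint reads when early mortality differs between arms. Fewer early deaths on alteplase would mean that the estimate understates the benefit. More early deaths on alteplase would mean that it looks better than the patients' outcomes justify. The Day 6 window covers the planned infusion days, so early treatment-related deaths would fall inside it.

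**Working it through.** **Step 1: the rules side by side.**

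| Analysis | Score for a death |
|---|---|
| Part 2 PaO2/FiO2, main ANCOVA (5.2.2, 7.5.2) | last value before death |
| Part 2 PaO2/FiO2, sensitivity analysis (7.5.2) | same value, covariates removed |
| Part 2 oxygen-free days (5.2.2) | 0, the worst value |
| Part 2 length of stay (5.2.2) | 28, the worst value |
| Part 1 PaO2/FiO2, main Hodges-Lehmann and Wilcoxon (5.2.2, 7.5.2) | failure |
| Part 1 PaO2/FiO2, sensitivity ANCOVA (7.5.2) | last value before death |

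The Part 1 sensitivity rule became the Part 2 main rule, and the death-as-failure analysis has no counterpart in Part 2.

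**Step 2: how many early deaths.** The plan gives no figure for this endpoint to reproduce. Protocol 7.5 gives about 140 alteplase and 70 SOC patients in the NIV cohort, with assumed Day 28 mortality of 9% and 25%. As a check on these inputs, the stated 85% power for mortality reproduces at 85.1% (two proportions, pooled variance). The share of deaths falling before Day 6 is not given, so it is an assumption here.

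Expected early deaths = n × Day 28 mortality × share before Day 6.

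- Share 5/28 (deaths spread evenly): SOC 70 × 0.25 × 5/28 = 3.1 (4.5%); alteplase 140 × 0.09 × 5/28 = 2.3 (1.6%).
- Share 5% to 35%: SOC 0.9 to 6.1; alteplase 0.6 to 4.4.

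**Step 3: effect on the mean under the planning rates.** Suppose a death were instead scored 50 to 150 mmHg below the last value (assumed). The shift in the mean difference is (0.25 − 0.09) × share × penalty.

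- Share 5/28: 0.16 × 5/28 × 50 = 1.4 mmHg, up to 0.16 × 5/28 × 150 = 4.3 mmHg.
- Full range: 0.16 × 0.05 × 50 = 0.4 mmHg, up to 0.16 × 0.35 × 150 = 8.4 mmHg.

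**Step 4: early deaths running against alteplase.** All inputs except the sample sizes are assumptions: early deaths 6% on alteplase and 2% on SOC, survivor mean change 30 mmHg on SOC and 55 on alteplase (a 25 mmHg benefit), mean change at death −20, SD 70. The death rates are roughly the mirror image of the 1.6% and 4.5% in Step 2.

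Expected means under the planned rule:

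- Alteplase: 0.94 × 55 + 0.06 × (−20) = 50.5.
- SOC: 0.98 × 30 + 0.02 × (−20) = 29.0.
- Difference: 21.5 mmHg. A threefold early death rate removes only 3.5 of the 25 mmHg.

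Simulated share of trials declaring benefit at two-sided 5%, over a range of covariate strength:

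- Last value before death: about 52-64%.
- Deaths ranked worst: about 38-46%.

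With 3,000 replicates the Monte Carlo standard error near 50% is √(0.25/3000), about 0.9 percentage points.

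**The case against.** The case for leaving the rule alone is substantial.

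- **The wording of 6.6 is loose.** It says death will be considered and then defers to Section 5, where a dedicated bullet exists. A reader might infer a broken promise to count death as a bad outcome in every endpoint, but the text does not go that far. An unstated while-alive strategy is a possible reading. What stands is that a rule giving death no weight as an unfavourable state sits awkwardly with that sentence, and nothing in the SAP names the strategy.
- **The ANCOVA comes from the protocol.** An unadjusted Wilcoxon as the main analysis would depart from protocol 7.2.3. This stands, and it is why the fix keeps the ANCOVA.
- **Early deaths should be few.** The SAP says so, and patients not expected to survive more than 48 hours are excluded. Using the worst daily value also captures some decline before death, more fully than the Part 1 daily average did. This limits the size of the problem without removing it.
- **Ranking deaths worst is no power gain.** A reader might infer one. With 2% early deaths on alteplase, 6% on SOC and a 25 mmHg benefit, an unadjusted t-test on the last value has 72% power and a rank test 76%. The plan is an adjusted ANCOVA, however. At an assumed baseline-to-change correlation of 0.3, planned power is 73-76% against 74-75% for the unadjusted rank test. At 0.5 it is 82-83% against 75%. The advantage vanishes or reverses.
- **Ranking alone would not expose harm.** With 6% early deaths on alteplase, 2% on SOC and no survivor benefit, the planned method shows about −2 mmHg and the ranked method about −5 to −6. Rejection rates are only 5-6% and 7-8%.

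**Conclusion.** The point holds as a minor one. Part 2 has no analysis of PaO2/FiO2 change in which an early death counts against the arm where it occurred, and this is out of line with section 6.6, with the two sibling endpoints and with Part 1. What an added analysis buys is protection from bias when early deaths differ by arm. In the assumed adverse scenario the chance of declaring benefit falls from about 52-64% to 38-46%. That scenario implies 0.06 × 140 = 8.4 early deaths on alteplase, more than the SAP appears to expect, so it marks what could happen and is not a forecast. Under the protocol's own mortality assumptions the rule works against alteplase, by a few mmHg.

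A reader might infer that the trial could miss a fatal early harm. The documents do not support that. All-cause mortality, and death or mechanical ventilation, both at Day 28, are key secondary endpoints in the test hierarchy. Deaths are outcome events under protocol 5.2.6.1.3, and the DMC receives fatal bleeds for immediate evaluation (protocol 8.7). The distortion is confined to one non-confirmatory endpoint.

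**What to change.** - Keep the protocol's ANCOVA on the last value, and state in SAP 5.2.2 and 7.5.2 that it is a while-alive estimate. Say what happens when no post-baseline ratio precedes death.
- Pre-specify alongside it a rank-based analysis with deaths before Day 6 ranked worst. Either carry over the Part 1 Wilcoxon with Hodges-Lehmann estimate, or use a covariate-adjusted ANCOVA on ranks, which keeps the adjustment.
- Qualify the sentence in 6.6 so that it agrees with the rule for this endpoint.
- If the rank analysis is made the main one, record it in SAP Section 4 as a change from protocol 7.2.3.

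The cost is SAP wording and one more analysis, with no new data. The Wilcoxon version gives up covariate adjustment; the rank ANCOVA does not.
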